5.2.4 Replacement of Subjects in DLT Evaluation Period

In order to determine safety, all subjects selected must meet the criteria for evaluability for Cycle 1. Subjects are considered non-evaluable and will be replaced if:

- They are enrolled but not treated
- They discontinue from the trial prior to completing all the safety evaluations for reasons other than treatment-related adverse events
- They receive less than 90% of the total MK-1966 or SD-101 in Cycle 1 (e.g., because the infusion had to be discontinued due to an infusion reaction) and did not experience a DLT

Non-evaluable subjects will not be counted toward the cohort total for DLT evaluation.

If a subject experiences a DLT in Cycle 1, trial treatment may be discontinued following discussion between the sponsor and Investigator. However, if the subject is deriving clinical benefit from the trial treatment, the subject may be allowed to continue after discussion between the sponsor and the Investigator.

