5.2.1.2 Dose Escalation

Enrollment to Arm A, (MK-1966 with SD-101) will begin at the 70 mg for MK-1966 and 1 mg for SD-101. The initial dose combination of SD-101 and MK-1966 will test the tolerability of administering both agents in subjects with advanced tumors. The following three dosing cohorts were chosen with administration of the higher fixed dose of SD-101 to increase immune activation combined with escalating doses of MK-1966. All dose levels in Part A will follow 3+3 design. Dose escalation of MK-1966 will continue to identify a preliminary MTD or MAD.

The dosing for each cohort is as follows:

- 1) 1 mg SD-101 intratumorally and 70 mg MK-1966 intravenously
- 2) 4 mg SD-101 intratumorally and 70 mg MK-1966 intravenously
- 3) 4 mg SD-101 intratumorally and 210 mg MK-1966 intravenously
- 4) 4 mg SD-101 intratumorally and 700 mg MK-1966 intravenously

Note, if the 4 mg SD-101 and 70 mg MK-1966 combination (cohort 2) is not tolerated, then SD-101 will be de-escalated to a 1 mg dose for subsequent cohorts (3 & 4). The study will include up to four dosing cohorts for SD-101 and MK-1966.

5.2.1.2.1 3+3 Dose Escalation

During 3+3 dose escalation, at least 2 days of observation will occur between each of the first 3 subjects at each dose level.

Dose escalation will increase in increments of approximately 3 fold.

The rules applied for the preliminary dose finding using the 3+3 design are as follows:

An initial cohort of 3 subjects is enrolled.

- If 0/3 subjects develops a DLT, escalation to the next dose will occur.
- If 1/3 subjects develops a DLT, another 3 subjects will be enrolled at this dose level.
 - If 0 of the 3 new subjects develops a DLT (for a total of 1/6 subjects with a DLT at this dose level), escalation to the next dose level will occur.

- If ≥ 1 of the 3 new subjects develops a DLT (for a total of $\geq 2/6$ subjects with a DLT at this dose level), the dose escalation stage of the trial will be terminated.

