5.2.2 Definition of Dose Limiting Toxicity

DLT's will be defined from toxicities observed during the first cycle of treatment (21 days) for each dose level. See Section 5.2.4 for rules on replacement of subjects in the DLT period. The occurrence of any of the following toxicities during Cycle 1, if assessed by the Investigator to be possibly, probably or definitely related to MK-1966 or SD-101 in Arm A, will be considered a DLT:

1. Grade 4 non-hematologic toxicity (not laboratory)
2. Grade 4 hematologic toxicity lasting \geq 7 days, except thrombocytopenia
 - a. Grade 4 thrombocytopenia of any duration
 - b. Grade 3 thrombocytopenia is a DLT if associated with bleeding:
3. Grade 3 non-hematologic toxicity (not laboratory) lasting $>$ 3 days despite optimal supportive care. Grade 3 nausea or vomiting will be considered a DLT if lasting more than 3 days despite optimal supportive care.
4. Any Grade 3 or Grade 4 non-hematologic laboratory abnormality, if
 - medical intervention is required, or
 - the abnormality leads to hospitalization, or
 - the abnormality persists for $>$ 1 week
5. Febrile neutropenia Grade 3 or Grade 4
6. Any drug-related AE which caused subject to discontinue treatment during Cycle 1
7. Grade 5 toxicity
8. Delay in initiation of Cycle 2 for $>$ 2 weeks due to study drug-related toxicity

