5.5.2 Prohibited Concomitant Medications

Subjects are prohibited from receiving the following therapies during the Screening, and Treatment Phases of this trial:

- Immunotherapy not specified in this protocol.
- Antineoplastic systemic chemotherapy or biological therapy. Investigational agents not specified in this protocol.
- Radiation therapy; radiotherapy for symptom management is allowed.
- Live vaccines within 30 days prior to the first dose of trial treatment and while participating in the trial. Examples of live vaccines include, but are not limited to, the following: measles, mumps, rubella, chicken pox, yellow fever, rabies, BCG, and typhoid vaccine. Seasonal influenza vaccines for injection are generally killed virus vaccines and are allowed. However, intranasal influenza vaccines (e.g. Flu - Mist®) are live attenuated vaccines, and are not allowed.

Glucocorticoids for any purpose other than to modulate symptoms from an adverse event. Glucocorticoids must be below 10 mg daily to restart SD-101 and/or MK-1966 dosing. Chronic systemic replacement doses of steroids are allowed. Inhaled steroids for management of asthma are allowed.

Subjects who, in the assessment by the investigator, require the use of any of the aforementioned treatments for clinical management should be removed from the trial. Subjects may receive other medications that the investigator deems to be medically necessary.

There are no prohibited therapies during the Follow-up visits.

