8.5 Analysis Populations

8.5.1 Safety Analysis Populations

The All-Patients-as-Treated (APaT) population will be used for the analysis of safety data in this study. The APaT population consists of all subjects who received at least one dose of study treatment. In case of treatment administration errors, subjects will be analyzed according to the treatment they actually received. For DLT evaluation, APaT subjects that were observed for safety for 21 days after the first dose of assigned treatment or experienced a DLT prior to 21 days after the first dose of assigned treatment will be used.

At least one laboratory or vital sign measurement obtained subsequent to at least one dose of study treatment is required for inclusion in the analysis of each specific parameter. To assess change from baseline, a baseline measurement is also required.

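### Section 5.2.4 does not exempt subjects who already had a DLT from its early-leaver replacement rule, so read literally it can drop an observed DLT that Section 8.5.1 keeps

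*Combined protocol and SAP*

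**What the plan says.** Section 5.2.4 opens its list with "Subjects are considered non-evaluable and will be replaced if" and gives three conditions:

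1. The subject was enrolled but never treated.
2. "They discontinue from the trial prior to completing all the safety evaluations for reasons other than treatment-related adverse events".
3. The subject received less than 90% of either drug in Cycle 1 "and did not experience a DLT".

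The consequence follows: "Non-evaluable subjects will not be counted toward the cohort total for DLT evaluation".

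Section 5.2.2 sets the window: "DLT's will be defined from toxicities observed during the first cycle of treatment (21 days) for each dose level". The 3+3 rules in Section 5.2.1.2.1 turn on single events, for example: "If 1/3 subjects develops a DLT, another 3 subjects will be enrolled at this dose level". A total of 1/6 then escalates and 2/6 or more stops. Section 5.2.1.2.2 applies Table 6 by setting the number of DLT-evaluable subjects against the number with a DLT. Confirmation ends when 20 subjects at a dose have at most 7 DLTs.

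The SAP defines the DLT evaluation set separately. Under Section 8.5.1, treated subjects who were observed for safety for 21 days "or experienced a DLT prior to 21 days after the first dose of assigned treatment will be used".

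**The concern.** A DLT that has been seen stays informative when the subject later leaves for an unrelated reason. What is lost by leaving early is the rest of the observation window, and that matters only for subjects who have had no DLT so far. The third condition of Section 5.2.4 respects this; the second does not.

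Take a subject who has a DLT on Day 5 and withdraws consent on Day 15, giving some other reason. The subject has left the trial before the safety evaluations were complete, and the stated reason is not a treatment-related adverse event. By the words of the second condition the subject is non-evaluable and is replaced. Nothing in Section 5.2.1.2 or Table 6 restores the event.

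At stake is whether the next subjects receive a higher MK-1966 dose on an understated toxicity count, and whether the reported DLT rate describes the same subjects as the dose decisions did. Section 7.1.2.1 plans no external safety reviewer, so the written counting rule carries much of the weight.

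**Working it through.** **The plan's own figure.** Table 12 is the only stated DLT figure that depends on the count. With the Beta(1,1) prior given under Table 6, 6 DLTs in 20 subjects give a Beta(7, 15) posterior. Its mode is (7 − 1)/(22 − 2) = 0.30 and its 80% highest-density interval is 0.185 to 0.435, as printed. All six rows reproduce this way. Table 12 takes the count as given, so it is not itself in error here.

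**The three rules applied to one subject** (treated, DLT in Cycle 1, then leaves the trial for a reason other than a treatment-related adverse event):

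- Section 5.2.4, second condition: non-evaluable, not counted, replaced.
- Section 5.2.4, third condition: would not remove the subject, because of the DLT.
- Section 8.5.1: in the DLT evaluation set.

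**Effect on a single decision.** Remove one DLT and assume that the replacement has none. Section 8.5.1 keeps both the removed subject and the replacement, so it adds 1 to the numerator and 1 to the denominator of the 5.2.4 count.

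| All DLTs counted, no replacement | Count under literal 5.2.4 | Count under 8.5.1 | Change in decision |
|---|---|---|---|
| 1/3 | 0/3 | 1/4 | escalate instead of adding 3 subjects |
| 2/6 | 1/6 | 2/7 | escalate instead of stop |
| 8/20 | 7/20 | 8/21 | within the limit of 7/20 instead of above it |

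**Illustration of the average effect.** Let p be the true DLT rate and q the share of subjects with a DLT who leave this way. The documents give no q, so it is an assumption throughout. If no DLT-free subject leaves, the DLT rate among counted subjects is

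p′ = p(1 − q) / [p(1 − q) + (1 − p)] = p(1 − q)/(1 − pq).

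The 3+3 escalates from a dose with probability (1 − p)³ + 3p(1 − p)²(1 − p)³ = (1 − p)³ + 3p(1 − p)⁵.

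- p = 0.40, q = 0: 0.216 + 1.2 × 0.07776 = 0.309.
- p = 0.40, q = 0.10: p′ = 0.36/0.96 = 0.375, giving 0.244 + 0.107 = 0.351.
- p = 0.40, q = 0.05 and 0.20: 0.330 and 0.401.
- p = 0.30 (the target rate), q = 0, 0.05, 0.10 and 0.20: 0.494, 0.516, 0.539 and 0.588.

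For the limit of 7/20, treat the 20 as a simple binomial sample and ignore earlier Table 6 moves. At p = 0.40 the chance of 7 or fewer DLTs is 0.416 with q = 0, 0.508 with q = 0.10 and 0.609 with q = 0.20.

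If DLT-free subjects leave at the same rate q, p′ = p(1 − q)/[(p + 1 − p)(1 − q)] = p, and the average count does not shift. The individual cohort's decision still ignores a known DLT.

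**The case against.** A reader might infer that the protocol deliberately declares such subjects non-evaluable even after a DLT, as a design choice to discard observed toxicity. The documents do not support that. The second condition is silent on DLTs, and the problem arises only from an omitted exception. Section 8.5.1 says the opposite for DLT evaluation. A DLT must be judged drug-related (Section 5.2.2), so a subject who leaves because of it falls outside the second condition and stays counted.

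The affected group is also narrow. Section 5.9 makes most discontinuations treatment-only, with monitoring in the trial allowed to continue, and lists only withdrawal of consent as a mandatory exit from the trial. Section 5.5.2 says that subjects who "require the use of any of the aforementioned treatments for clinical management should be removed from the trial", but its prohibitions cover screening and treatment and not the follow-up visits. A subject already off treatment after a severe toxicity may therefore not be reached by it. Sections 4.2.3.5 (lymphoma subjects needing another therapy) and 5.8.3 (pregnancy) add rare routes. Scheduled imaging starts at week 12, so few progression-driven exits should fall within 21 days.

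Finally, under Section 7.1.2.1 the sponsor and investigators review each cohort before the next opens, and they would know of the DLT. They would probably not escalate past it unremarked.

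All of this limits the size of the problem. It does not remove the conflict: Section 8.5.1 defines an analysis population, and nothing says that it overrides Section 5.2.4 for cohort counting and replacement. Relying on reviewers to set aside a written rule is no substitute for correcting it.

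**Conclusion.** Wrong as written: an internal inconsistency in the DLT counting rule. The second condition of Section 5.2.4, taken literally, gives a count that disagrees with the third condition beside it and with Section 8.5.1.

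The conclusion rests on the wording alone and needs no value of q. One case is enough to change one cohort's decision, provided the replacement has no DLT; at a true rate of 40% that has probability 0.60.

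The rise from 30.9% to 35.1% is an illustration under q = 10% with no DLT-free leavers. A reader might take it as the expected effect on this trial, but the documents give no basis for any q, and the average shift is nil if leaving is unrelated to DLT status. No stated sample size or precision figure changes.

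**What to change.** Reconcile Section 5.2.4 with Section 8.5.1:

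- Add "and did not experience a DLT" to the end of the second condition, as the third already has it.
- Add one sentence: every treated subject with a DLT in the DLT period is evaluable and counts in the 3+3 and Table 6 decisions, whatever the later reason for leaving the trial.

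The cost is a short protocol amendment, with no extra subjects, procedures or change of dose.

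The downside is a slightly conservative count, because DLT-free leavers are still replaced while leavers with a DLT are kept. If a share r of DLT-free subjects leave, the counted rate is p/[1 − (1 − p)r]. With p = 0.30 and an assumed r = 0.10 this is 0.30/0.93 = 0.323. In a first-in-human escalation that is the safer direction of error.

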5.2.5 Timing of Dose Administration

Minimal dosing interval between SD-101 dosing must be 5 days. Trial treatment may be administered up to 3 days before or 5 days after the scheduled Day 1 of each cycle, beginning in Cycle 3. Cycle 2 Day 1 may be administered up to 1 day after the scheduled day 1. In addition, dosing interruptions are permitted in the case of medical / surgical events or logistical reasons not related to study therapy (e.g., elective surgery, unrelated medical events, patient vacation, and/or holidays). Subjects should be placed back on study therapy

within 2 weeks of the scheduled interruption, unless otherwise discussed with the Sponsor. The reason for interruption should be documented in the patient's study record.

5.2.6 Trial Blinding/Masking

This is an open-label trial; therefore, the Sponsor, investigator and subject will know the treatment administered.

5.3 Randomization or Treatment Allocation

In Parts A, B and C treatment allocation will manually occur by non-random assignment.

5.4 Stratification

No stratification based on age, sex or other characteristics will be used in this trial.

5.5 Concomitant Medications/Vaccinations (Allowed & Prohibited)

Medications or vaccinations specifically prohibited in the exclusion criteria are not allowed during the ongoing trial. If there is a clinical indication for any medication or vaccination specifically prohibited during the trial, discontinuation from trial therapy or vaccination may be required. The investigator should discuss any questions regarding this with the Sponsor Clinical Director. The final decision on any supportive therapy or vaccination rests with the investigator and/or the subject's primary physician. However, the decision to continue the subject on trial therapy or vaccination schedule requires the mutual agreement of the investigator, the Sponsor and the subject.

5.5.1 Acceptable Concomitant Medication

All treatments that the investigator considers necessary for a subject's welfare may be administered at the discretion of the investigator in keeping with the community standards of medical care. All concomitant medication will be recorded on the case report form (CRF) including all prescription, over-the-counter (OTC), herbal supplements, and IV medications and fluids. If changes occur during the trial period, documentation of drug dosage, frequency, route, and date will also be included on the CRF.

Palliative and supportive care is permitted during the course of the trial for underlying medical conditions and management of symptoms. Surgery or radiotherapy for tumor control is not permitted during the study; however, radiotherapy or procedures for symptom management is allowed.

All concomitant medications received within 30 days before the first dose of trial treatment through the Safety Follow-up Visit should be recorded. After the Safety Follow-up Visit record all medications taken for SAEs as defined in Section 7.2.

5.5.2 Prohibited Concomitant Medications

Subjects are prohibited from receiving the following therapies during the Screening, and Treatment Phases of this trial:

- Immunotherapy not specified in this protocol.
- Antineoplastic systemic chemotherapy or biological therapy. Investigational agents not specified in this protocol.
- Radiation therapy; radiotherapy for symptom management is allowed.
- Live vaccines within 30 days prior to the first dose of trial treatment and while participating in the trial. Examples of live vaccines include, but are not limited to, the following: measles, mumps, rubella, chicken pox, yellow fever, rabies, BCG, and typhoid vaccine. Seasonal influenza vaccines for injection are generally killed virus vaccines and are allowed. However, intranasal influenza vaccines (e.g. Flu - Mist®) are live attenuated vaccines, and are not allowed.

Glucocorticoids for any purpose other than to modulate symptoms from an adverse event. Glucocorticoids must be below 10 mg daily to restart SD-101 and/or MK-1966 dosing. Chronic systemic replacement doses of steroids are allowed. Inhaled steroids for management of asthma are allowed.

Subjects who, in the assessment by the investigator, require the use of any of the aforementioned treatments for clinical management should be removed from the trial. Subjects may receive other medications that the investigator deems to be medically necessary.

There are no prohibited therapies during the Follow-up visits.

